6.3. Ifosfamide (Ifex®)

Supplier: Commercially available and will not be provided for this study.

Mechanism of Action: Ifosfamide is activated in the liver by microsomal enzymes and the subsequent ifosfamide mustard causes direct alkylation of DNA.

Formulation: Ifosfamide is supplied in single dose vials for constitution and administration by IV infusion. Each contains 1 gram or 3 grams of sterile ifosfamide.

Storage: The dry powder may be stored at room temperature.

Preparation: Injections are prepared by adding sterile water to the vial. The 1-gram dose is mixed with 20 mL and the 3-gram dose with 60 mL for a final concentration of 50 mg/mL.

Toxicity: Alopecia, nausea and vomiting, hematuria, gross hematuria, CNS toxicity, infection, renal dysfunction, allergic reactions and at high doses, cardiotoxicity.

6.4. Carboplatin (Paraplatin®)

Supplier: Commercially available and will not be provided for this study.

Mechanism of Action: Carboplatin binds to DNA and causes cross-linking with a non-cell cycle dependent tumor cell lysis. It inhibits DNA synthesis by altering the template via the formation of intrastrand cross-links.

Formulation: Carboplatin is available in 10 mg/mL solution in 50, 150, 450, 600 mg vials.

Storage: Unopened vials are stable for the life indicated on the insert if protected from light.

Preparation: Per Institute standard.

Toxicity: Myelosuppression, nausea, vomiting, peripheral neuropathy, ototoxicity, hepatic toxicity, electrolyte abnormalities, hypomagnesemia, hypocalcemia, and allergic reactions.

6.5. VP-16 (etoposide, VePesid®)

Supplier: Commercially available and will not be provided for this study.

Mechanism of Action: Induction of an irreversible blockade of cells in the premitotic phases of the cell cycle leading to accumulation of cells in late S or G2 phases. This mechanism is secondary to interference of the scissors-reunion reaction of the enzyme topoisomerase II.

Formulation: VP-16 injection is available in 100-mg (5-mL) sterile multiple-dose vials. The pH is 3-4. Each mL contains 20-mg etoposide, 2-mg citric acid, 30-mg benzyl alcohol, 80-mg polysorbate 80, 650-mg polyethylene glycol 300 and 30.5% alcohol.

Storage: Unopened vials of VP-16 are stable for 24 months at room temperature. Vials are diluted as recommended to a concentration of 0.2 mg/mL or 0.4 mg/mL and are stable for 96 hours and 48 hours respectively, at room temperature under normal light in both plastic and glass containers.

Preparation: As per Institute standard intravenous infusion over 2 hours.

Toxicity: Leukopenia, thrombocytopenia, alopecia, nausea, vomiting, headache, fever, hypotension, anorexia, and allergic reactions.

6.6. Mesna (Mesnex®)

Supplier: Commercially available and will not be provided for this study.

Mechanism of Action: Mesna was developed as a prophylactic agent to inhibit hemorrhagic cystitis induced by ifosfamide and is analogous to the cysteine-cystine system; mesna is rapidly metabolized to mesna disulfide and acts as a free radical scavenger.

Formulation: Mesna is a sterile preservative free aqueous solution of clear, colorless appearance in clear glass vials for IV administration. Mesna injection contains 100 mg/mL Mesna, 0.25 mg/mL acetate disodium, and sodium hydroxide to maintain pH 6.5-8.5.

Storage: Diluted solutions are chemically and physically stable for 24 hours at room temperature. It is recommended that solutions be refrigerated and used within 6 hours.

Preparation: For IV administration the drug is diluted in sterile solution to make a final concentration as per Institute standard.

Toxicity: Nausea, vomiting, diarrhea

6.7. Neulasta® (Pegfilgrastim, G-CSF, Neupogen, Filgrastim-sndz and biosimilars)

Supplier: Commercially available and will not be provided for this study.

Mechanism of action: Pegfilgrastim is a human protein, which is involved in the promotion of the growth and maturation of granulocytic progenitors and the stimulation of functional activity. It is a covalent conjugate of recombinant methionyl human G-CSF (Filgrastim) and monomethoxypolyethylene glycol

Formulation: Available as a pegylated recombinant DNA product supplied as 0.6 mL prefilled syringe containing clear colorless sterile protein solution.

Storage: It can be stored at 2°C - 8°C and is stable for at least 30 months.

Toxicity: Bone pain, exacerbation of preexisting autoimmune disorders, transient and reversible changes in alkaline phosphatase, uric acid and LDH, nausea, fatigue, alopecia, diarrhea, vomiting, constipation, fever, anorexia, skeletal pain, headache, taste perversion, dyspepsia,

myalgia, insomnia, abdominal pain, arthralgia, generalized weakness, peripheral edema, dizziness, granulocytopenia, stomatitis, mucositis, and neutropenic fever

7. TREATMENT PLAN

7.1. Preparation and Administration

Treatment will be administered in an outpatient and inpatient basis. Appropriate dose modifications are described in **Section 7.4**. No other investigational or commercial drugs or therapies other than those described below may be administered with the intent to treat the patient.

7.2. General Guidelines

Prior to initiating therapy, placement of mediport or a multi-lumen indwelling intravenous catheter is required. All patients will be given allopurinol 300 mg/day PO starting at least one day prior to Treatment 1 (Day 0) and then 300 mg/day PO for Day 1 through Day 10 of the first cycle. Allopurinol length of therapy may be changed at discretion of the investigator (e.g., the presence of tumor lysis syndrome). If patient cannot receive Allopurinol for any reason, a different drug may be used for the prevention of tumor lysis syndrome at the discretion of the PI.

7.3. Criteria for Retreatment

The following laboratory parameters must be met before starting Cycles 2 and Cycle 3:

- Begin subsequent cycles no sooner than Day 22 but no later than Day 36 (If a subject is delayed beyond Day 36, contact the Principle Investigator or designee from Roswell Park)
- ANC \geq 1000/ μ L without G-CSF
- Platelets \geq 50,000/ μ L
- Serum creatinine \leq 2.0 mg/dL
- Total bilirubin \leq 2.0 mg/dL (unless due to disease involvement with DLBCL or Gilbert's syndrome).

Serum chemistry values, including creatinine, must be obtained (within 24 hours) and reviewed prior to each dose of carfilzomib. Carfilzomib must be held for subjects with a CrCL $<$ 30 mL/min at any time during study participation. Subjects with active or suspected infection of any kind that required systemic treatment should not be dosed with carfilzomib until the infection has resolved and if being treated with anti-infective, the course of antibiotics has been completed.

7.4. Dose Modifications

7.4.1. Definition of Dose-Limiting Toxicity

For this protocol, a DLT will be defined by the occurrence of the following toxicity, related to study drug, within cycle 1 of treatment. Patients that experience a DLT will be continued on treatment, per PI discretion, at one level of dose reduction.

- Any \geq Grade 3 non-hematologic adverse event attributed (definitely, probably, or possibly) during C-R-ICE therapy and meeting the following criteria and for hematologic toxicity see **Section 0**.

7.4.1.1 Non-Hematologic Toxicity

For non-hematologic toxicities, DLT will be defined as any CTCAE v4.0 Grade 3 or greater toxicity, except for:

- Grade 3 or Grade 4 nausea and vomiting lasting less than 72 hours after the last dose of chemotherapy with use of standard anti-emetic therapy.
- Grade 3 non-hematologic laboratory abnormalities that resolve to Grade 1 or baseline (if the patient entered the study with existing toxicity) within 14 days.
- In the event that Grade 3 or Grade 4 adverse events are obviously unrelated to study drug and thus not DLT, the principal investigator will determine whether dose escalation or cohort expansion is required.

7.4.1.2 Hematologic Toxicity

DLT for hematologic toxicity, using CTCAE v4.0, will be defined as:

- Any hematologic toxicity that causes a dose-delay of > 2 weeks (i.e., $>$ Day + 36) of the intended next dose will also be considered at DLT.

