7.4.1.3 Criteria for Dose Escalation

Dose escalation will proceed within each cohort according to the following scheme in **Table 2**.

Patients who do not have a DLT and who do not complete Cycle 1 of treatment or more if appropriate will be replaced in the study.

Management and dose modifications associated with the above AEs are outlined in **Section 7.4**.

Table 2. Dose Escalation Scheme

Number of Patients with a Dose-Limiting Toxicity at a Given Dose Level	Escalation Decision Rule
0 out of 3	Enter 3 patients at the next dose level. If there are no dose-limiting toxicities found after completing all dose levels, an additional 3 patients will be enrolled at the maximally administered dose. If this dose level is determined to be a safe dose (≤ 1 out of 6 dose-limiting toxicities), it will then be used in the expansion phase.
≥ 2	Dose escalation will be stopped. This dose level will be declared the maximally administered dose (highest dose administered). Three additional patients will be entered at the next lowest dose level if only 3 patients were treated previously at that dose.
1 out of 3	Enter at least 3 more patients at this dose level. If 0 of these 3 patients experience a dose-limiting toxicity, proceed to the next dose level. If 1 or more of this group suffer a dose-limiting toxicity, then dose escalation is stopped, and this dose is declared the maximally administered dose. Three additional patients will be entered at the next lowest dose level if only 3 patients were treated previously at that dose.
≤ 1 out of 6 at highest dose level	This is generally the recommended Phase Ib dose. At least 6 patients must be entered at the recommended Phase Ib dose.

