7.4.2.8 Other Conditions Delaying Treatment

If posterior reversible encephalopathy syndrome (PRES) is suspected, carfilzomib should be held. The patient should then be evaluated with MRI and for onset of visual or neurological symptoms suggestive of PRES. If PRES is confirmed, carfilzomib should be permanently discontinued. If a diagnosis of PRES is excluded, carfilzomib may be restarted per the discretion of the PI.

Carfilzomib should be held if thrombotic microangiopathy (TMA) is suspected and patient should be managed per institutional standard of care, which may include plasma exchange, if appropriate. If TMA is confirmed, carfilzomib should be permanently discontinued. If TMA is ruled out, then carfilzomib may be restarted per the discretion of the PI.

If the patient experiences a hypertensive crisis, carfilzomib should be held until the resolution of the event to the patient's baseline. Carfilzomib may then be restarted at 1 dose decrement.

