13 STATISTICAL METHODOLOGY

This is single-center, open-label, prospective Phase I/Ib clinical trial evaluating the safety, efficacy, and pharmacokinetics/pharmacodynamics of carfilzomib and standard R-ICE combination therapy in adult patients with relapsed/refractory diffuse large B-cell lymphoma. The statistical design is based on a dose-finding algorithm to determine the maximal tolerated dose (MTD) of the study regimen and an assessment of the efficacy of the treatment for patients as compared to an external standard, i.e., R-ICE historical control. All enrolled patients will receive the study drug and initiation of the treatment should take place as soon as possible following study enrollment. A maximum total of up to 21 evaluable patients will be enrolled in the Phase I of this study, and a total of 9 evaluable patients will be enrolled in the Phase Ib portion of the study. An evaluable subject is defined as a subject who meets eligibility requirements and who does not discontinue prior to end of Cycle 1 for reasons other than DLTs for Phase I or who completes at least 1 cycle of planned therapy for Phase Ib. If a subject signs

an Informed Consent and does not receive treatment, the subject will not be classified as evaluable and will be replaced. Unevaluable patients will be replaced. Analyses will be performed with a focus on estimation of specific clinically important parameters for use in the planning of larger subsequent comparative trials designed to fully assess efficacy and safety.

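### Read literally, the hematologic DLT definition and the replacement rule can drop a Cycle 1 hematologic stop from the 3+3 count, so the DLT count behind Dose Level 6 may be too low.

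*Combined protocol and SAP*

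**What the plan says.** Section 7.4.1 sets the window and attribution: "a DLT will be defined by the occurrence of the following toxicity, related to study drug, within cycle 1 of treatment". The criteria then split by toxicity class.

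- **Non-hematologic (7.4.1.1).** The rule is based on grade: "DLT will be defined as any CTCAE v4.0 Grade 3 or greater toxicity, except for" a short list of exceptions.
- **Hematologic (7.4.1.2).** The single bullet is based on delay: "Any hematologic toxicity that causes a dose-delay of" more than 2 weeks (beyond Day +36) "of the intended next dose will also be considered at DLT". It has no limb for grade, duration, discontinuation or death. Day 36 matches Section 7.3: "Begin subsequent cycles no sooner than Day 22 but no later than Day 36".
- **Replacement (7.4.1.3).** "Patients who do not have a DLT and who do not complete Cycle 1 of treatment or more if appropriate will be replaced".
- **Evaluability (Section 13).** An evaluable subject is an eligible one "who does not discontinue prior to end of Cycle 1 for reasons other than DLTs for Phase I". Unevaluable patients are replaced, and toxicity is not excepted.

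Section 8.5 lists treatment-related toxicity and investigator judgment among the reasons for stopping treatment, so such stops are foreseen. No section says how a hematologic stop is scored. Table 2 accepts a level at no more than 1 DLT in 6, and Section 4.1 sets the Phase Ib dose at Dose Level 6.

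**The concern.** A delay presupposes a next dose. If treatment ends, no next dose is intended, and a literal reader of 7.4.1.2 finds no DLT. The replacement rule then substitutes another patient. A toxicity severe enough to end treatment could thus score lower than one that postpones Cycle 2 by 15 days.

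The class of toxicity matters here. Section 7.4.2 describes thrombocytopenia with carfilzomib, and Sections 6.4 and 6.5 list myelosuppression for carboplatin and leukopenia and thrombocytopenia for etoposide. The maximum tolerated dose is the Phase I primary objective, Table 2 turns on 1 versus 2 events in 6, and 9 further patients are planned at the selected level.

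**Working it through.** The plan states no DLT rate, no DLT count by level and no operating characteristic for its 3+3 rule, so there is no figure to reproduce. The check has two parts.

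**1. Following a patient through the rules**

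| Course in Cycle 1 (drug-related hematologic toxicity) | 7.4.1.2 | 7.4.1.3 and Section 13 | Effect on the count |
|---|---|---|---|
| Next dose given after Day 36 | DLT | evaluable | 1 event in the numerator |
| (a) Treatment ends during Cycle 1, no delay beyond Day 36 | no DLT as written | unevaluable, replaced | leaves numerator and denominator |
| (b) Cycle 1 completed, withdrawn with unrecovered counts before Day 36 | no DLT as written | evaluable, not replaced | stays in the denominator as DLT-free |

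Route (b) is possible because 7.4.2.3 plans a cycle of 21 to 28 days, while the delay limit falls at Day 36.

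**2. What one patient, or an assumed rate, would do**

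One patient, starting from a level accepted at 1 of 6 = 16.7%:
- Route (a), one replaced stop counted among all treated: (1 + 1)/(6 + 1) = 2/7 = 28.6%.
- Route (b), one patient rescored: (1 + 1)/6 = 2/6 = 33.3%, above Table 2's limit of 1 in 6.

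A rate, for route (a) only. Let p be the true probability of an intolerable Cycle 1 toxicity and q the part of p that is uncounted and replaced. Both are assumptions, as the documents give neither. Patients are taken as independent and replacements as drawn from the same population.

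- Rate seen among evaluable patients: r = (p − q)/(1 − q)
- Chance that a level passes at no more than 1 of 6: P(r) = (1 − r)^6 + 6r(1 − r)^5

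In full for p = 20%, q = 10%: r = 0.10/0.90 = 11.1%. With all events counted, P = 0.8^6 + 6 × 0.2 × 0.8^5 = 0.262 + 0.393 = 65.5%. With the replaced events lost, P(0.111) = 86.3%.

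| p | q | rate seen | pass, all counted | pass, as written |
|---|---|---|---|---|
| any | 0% | p | unchanged | unchanged |
| 12% | 2% | 10.2% | 84% | 88% |
| 10% | 5% | 5.3% | 88.6% | 96.4% |
| 20% | 10% | 11.1% | 65.5% | 86.3% |
| 30% | 15% | 17.6% | 42.0% | 71.3% |
| 33% | 5% | 29.5% | 35.8% | 43.2% |
| 33% | 10% | 25.6% | 35.8% | 52.1% |
| 33% | 20% | 16.3% | 35.8% | 74.7% |

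The shift is always towards acceptance. Its size runs from nil at q = 0 to large at q = 20%. Nothing in the documents says where q lies.

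**The case against.** Several points on the other side are sound.

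- **The low-count rules lead to holds, not stops.** Sections 7.4.2, 7.4.2.3 and 8.1 hold or postpone treatment, and 7.3 asks for contact with the principal investigator beyond Day 36. Counts that stay low past Day 36 can fairly be read as a delay of more than 2 weeks, and so as a DLT, even if treatment then ends. Routes (a) and (b) therefore need an earlier stop, most likely under the general reasons in 8.5.
- **Some severe consequences are caught elsewhere.** Drug-related Grade 3 or higher non-hematologic consequences of low counts, such as infection, fall under 7.4.1.1. A reader might infer that the worst hematologic intolerance goes uncounted; the documents do not support that.
- **Thrombotic microangiopathy is a weak example.** Section 7.4.2.8 says "If TMA is confirmed, carfilzomib should be permanently discontinued", but lists the condition among other conditions, not under hematologic toxicity. The documents never class it for DLT purposes. If it is non-hematologic, a related Grade 3 or higher case is already a DLT. The point does not depend on it.
- **Text may have been lost.** The word also in the 7.4.1.2 bullet, and the reference in 7.4.1 to a Section 0, suggest that a companion criterion once stood there. That is a reason to repair the section, but it supplies no rule for a stop.
- **Events are recorded.** Section 11.1.3 reports all grades and attributions in Phase I, and Section 12 provides for safety review. That keeps the events visible but does not put them in the 3+3 count.
- **Dose Level 6 is already chosen.** A rewritten criterion cannot now serve as the decision rule. This limits the remedy to clarification and reporting.

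These points narrow the gap. None of them says how a Cycle 1 hematologic stop is counted.

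**Conclusion.** The concern holds in this form: the rules as written can remove a drug-related hematologic stop from the 3+3 count by replacement, or score it as DLT-free, and both errors favour escalation. The DLT count behind Dose Level 6 may therefore be too low.

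A reader might go further and infer that the count does omit such patients, or that it is biased downward at every level. The documents do not show either, because they report no DLTs, discontinuations or replacements at any level. If no such stop occurred, the count stands. Replacement also applies only to patients who leave before Cycle 1 is complete.

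One replaced stop would turn 16.7% into 28.6%. The pass probabilities above rest on assumed rates and show direction and possible range, not an estimate for this trial. The matter is worth correcting because it touches the Phase I primary objective and the answer is available at little cost from data already held.

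**What to change.** 1. Reconcile 7.4.1 (including its reference to Section 0), 7.4.1.2, 7.4.1.3 and Section 13, so that they say how a drug-related hematologic discontinuation or death in Cycle 1 is counted, and so that such a patient is not treated as unevaluable and replaced.
2. Report Phase I DLTs by dose level among all treated patients, beside the count among evaluable patients. List every replaced or withdrawn patient with dose level, timing and reason.
3. For Dose Level 6, keep the count made under the protocol and add, as a sensitivity analysis, the result with these patients counted as events. Label it post hoc.

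The cost is a few clarifying sentences and a re-tabulation of at most 21 evaluable Phase I patients plus any who were replaced. The stated DLT rate may become less favourable; if there were no such stops, the table shows that and strengthens the result. No dose or treatment rule is proposed.

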7.4.1.3 Criteria for Dose Escalation

Dose escalation will proceed within each cohort according to the following scheme in **Table 2**.

Patients who do not have a DLT and who do not complete Cycle 1 of treatment or more if appropriate will be replaced in the study.

Management and dose modifications associated with the above AEs are outlined in **Section 7.4**.

Table 2. Dose Escalation Scheme

Number of Patients with a Dose-Limiting Toxicity at a Given Dose Level	Escalation Decision Rule
0 out of 3	Enter 3 patients at the next dose level. If there are no dose-limiting toxicities found after completing all dose levels, an additional 3 patients will be enrolled at the maximally administered dose. If this dose level is determined to be a safe dose (≤ 1 out of 6 dose-limiting toxicities), it will then be used in the expansion phase.
≥ 2	Dose escalation will be stopped. This dose level will be declared the maximally administered dose (highest dose administered). Three additional patients will be entered at the next lowest dose level if only 3 patients were treated previously at that dose.
1 out of 3	Enter at least 3 more patients at this dose level. If 0 of these 3 patients experience a dose-limiting toxicity, proceed to the next dose level. If 1 or more of this group suffer a dose-limiting toxicity, then dose escalation is stopped, and this dose is declared the maximally administered dose. Three additional patients will be entered at the next lowest dose level if only 3 patients were treated previously at that dose.
≤ 1 out of 6 at highest dose level	This is generally the recommended Phase Ib dose. At least 6 patients must be entered at the recommended Phase Ib dose.

7.4.2 Treatment Delay Thrombocytopenia and Neutropenia

Carfilzomib is associated with thrombocytopenia. The thrombocytopenia pattern is cyclic with nadirs following the second dose each week and typically recovering prior to the initiation of the next treatment, similar to that observed with bortezomib. The severity of thrombocytopenia is related to the pretreatment platelet counts. Transfusions may be considered. The incidence of significant bleeding is $< 5\%$. Platelet counts should be monitored at a minimum prior to each cycle of treatment and more frequently if baseline counts are $>$ Grade 1. Severe neutropenia has been reported and may occur during treatment but is uncommon. Carfilzomib should be administered with caution to patients with ANC $< 1000/\text{mm}^3$ and the drug should be held for ANC $< 500/\text{mm}^3$. Febrile neutropenia is rare and carfilzomib should be held until the AE has resolved. In addition, patients with active infections or who are completing treatment for systemic infections should not receive carfilzomib until the infection has resolved.

7.4.2.1 Cardiac Disorders

Acute development or exacerbation of congestive heart failure and new onset of decreased left ventricular function have been reported, including reports in patients with no risk factors for decreased left ventricular ejection fraction. The incidence of heart failure events (acute pulmonary edema, cardiac failure, congestive cardiac failure, cardiogenic shock, pulmonary edema) is less than 8%. Patients with risk factors for or evidence of existing heart disease should be closely monitored throughout their treatment with carfilzomib. Carfilzomib should be held if CHF develops or appears to be exacerbated by treatment and may be resumed once the symptoms resolve. Consideration should be given to a reduction in dosage with gradual increase to full dose only if well tolerated. Ischemic heart disease and arrhythmias have also occurred. Dyspnea may occur in association with cardiac disorders. Patients who experience dyspnea

should be evaluated for the presence of associated conditions and management should be tailored to the appropriate treatment for the underlying disorder. The effect of carfilzomib on cardiac repolarization using the QTcF interval and the PK-PDn relationships shows no clear signal of any dose related effect. Serious cardiac reactions and even death may occur following the administration of carfilzomib.

